5.1.3 Study Follow-Up

Follow-Up Visit (V9) (LCIG Subjects not Continuing on Commercial Product)

For subjects who are not continuing on LCIG (through commercial sources in countries where LCIG is approved and marketed), the PEG-J tube will be removed following the End of Study activities. A follow-up clinic visit will occur approximately one week later.

Commercial Transition Visits (LCIG Subjects Continuing on Commercial Product)

Study subjects in the LCIG group who complete participation in the study and for whom continuation of treatment with LCIG is judged appropriate by the Investigator will continue to receive LCIG until transition to commercial product is coordinated with the Sponsor's commercial affiliate.

Additional visits every 12 weeks from Week 26 will be schedule to monitor subject safety and allow for drug resupply until the subject transfer to commercial LCIG. Refer to [Table 3](#) of Section [5.3.1.1](#) for list of assessments. Drug resupply visits will also occur at 6 week intervals between the every 12 week safety assessments.

Upon transfer of subjects to commercial LCIG the monitoring of such therapy will be the responsibility of the subject's personal physician. All necessary support will be provided by the Sponsor's local representative. Follow-up care in these circumstances will be based on the judgment of the subject's personal physician and no formal collection of data will be conducted except for regular ADR-reporting in accordance with local instructions.

OMT Subjects

Study subjects in the OMT group who complete participation in the study are eligible to transition to commercial LCIG after end of study procedures if judged appropriate by their personal physician. This transition is not study related.

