United States subjects in LCIG arm will continue to have study drug dispensation every 4 weeks and will have study visits at 3 and 6 months, or the day prior to transition to commercial if that happens before the scheduled study visits. United States subjects from the OMT arm will undergo the NJ (optional) and PEG-J procedures, titration, plus have visits at 2 weeks, 6 weeks, 3 months and 6 months post NJ or PEG-J, or the day prior to transition to commercial if that happens before the scheduled study visits. Subjects will receive study drug every 4 weeks. The Extension Period will last for a maximum of 6 months to allow for continuity of care while the transition to commercially available drug occurs.

Part 4: Follow-up period. For subjects who elect to discontinue LCIG treatment at any time during the study, the PEG-J tube will be removed following the End of Study activities. A follow-up clinic visit will occur approximately 1 week later. For study subjects who complete participation in the study and will continue to receive LCIG, subjects will return every 6 weeks to return used LCIG cassettes and be dispensed cassettes. Additional visits every 12 weeks from Week 26 will be scheduled to monitor subject safety and allow for drug resupply until the subject transfers to commercial LCIG.

Figure 1. Study Design Schematic (All Countries Except for United States and South Korea)

[figure not shown]
[figure not shown]
[figure not shown]

Figure 2. Study Design Schematic (United States)

Extension Period:

OMT Subjects

LCIG Subjects

[figure not shown]
[figure not shown]
[figure not shown]

Figure 3. Study Design Schematic (South Korea)

[figure not shown]

Extension Period:

OMT Subjects

LCIG Subjects

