For subjects randomized to the LCIG group, the date and time of the earliest LCIG tube placement (NJ or PEG-J) recorded on the Device Information eCRF will be considered

the treatment start reference date (REFDT1) and time (DMREFTM). The date of the last LCIG tube removal, or the date of the last LCIG infusion if there is no device removal in the 26-week randomized period will be considered as end of the LCIG 26-week randomized treatment period and the following day will be the post-treatment start reference date (REFEDT1). For LCIG subjects who enter the Extension Period, treatment start reference date in extension period (REFDT2) equals REFEDT1. The date of the last LCIG tube removal or the date the last LCIG infusion if there is no device removal, will be the post-treatment reference date (REFEDT2) of Extension Period.

For subjects in the OMT group, the date after randomization will be considered the treatment start reference date (REFDT1). The date of the final visit during 26-week randomized period will be considered the end of the OMT treatment period and the following day will be the post-treatment start reference date (REFEDT1). For OMT subjects who enter the Extension Period, the date of earliest LCIG tube placement (NJ or PEG-J) recorded on the Device Information eCRF will be considered the treatment start reference date (REFDT2) in Extension period. The date of the last LCIG tube removal, or the date the last LCIG infusion if there is no device removal, will be considered the end of the Extension Period and the following day will be the post-treatment start reference date (REFEDT2).

Study Days during 26-week randomized treatment period will be calculated based on the treatment start reference date (REFDT1). For time points before REFDT1, the Study Day = time point – REFDT1. For time points on or after REFDT1, the Study Day = time point – REFDT1 + 1. Thus, the Study Day is a negative value when the time point of interest is prior to REFDT1 and the Study Day is a positive value when the time point of interest is on or after REFDT1. There is no Study Day 0. The Study Day will be labeled as Rx Day on the data listings. Study Days during Extension Period will be calculated based on the Extension Period start reference date (REFDT2) with the same rule as in 26-week randomized treatment period. For OMT subjects who enter the Extension Period, the study day of Pre in Extension Period will be calculated based on REFDT2.

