6.4 Analysis by Planned Visit

A midpoint convention will be used to assign all observations to a planned visit based on the Study Day of the observation. If there are multiple observations on the same day, the average will be taken and considered the observation for the day. If more than one observation is assigned to a planned visit, the last observation will be selected and considered the observation for the planned visit.

The following Study Day windows will be used to assign efficacy and health outcome assessments to planned study visits during 26-week randomized treatment period.

Table 1. Analysis Windows for Efficacy Variables

Assessment	Planned Visit	Nominal Study Day	Study Day Range ^a
NMSS, PDSS-2, PDQ-8, PAS, GDS-15, UPDRS and King's PD Pain Scale	Baseline		≤ date of randomization
	Week 6	42	2 – 63
	Week 12	84	64 – 133
	Week 26	182	134 – 222
CGI-C and PGIC	Week 26	182	≥ 2

a. For subjects in LCIG group, all post-baseline assessments must also be after start of LCIG infusion through PEG-J and no more than 1 day after the date of the last LCIG infusion in the 26-week Treatment Period.

The following Study Day windows will be used to assign safety assessments to planned study visits.

Table 2. Analysis Windows for Safety Variables During the 26-Week Treatment Period

Assessment	Planned Visit	Nominal Study Day	Study Day Range ^a
Vital signs and weight	Baseline		≤ date of randomization
	Week 2	14	2 – 28
	Week 6	42	29 – 63
	Week 12	84	64 – 133
	Week 26	182	134 – 186
	Week 27 FU ^b	189	187 – 301
Clinical labs and Electrocardiograms	Baseline		≤ date of randomization
	Week 12	84	2 – 133
	Week 26	182	> 133
Special labs	Baseline		≤ date of randomization
	Week 12	84	2 – 133
	Week 26	182	134 – 231

- a. For subjects in LCIG group, all post-baseline assessments must also be no more than 1 day after the final PEG-J removal for subjects who have their study device removed after their last infusion of Study M12-927 LCIG.
- b. Applicable only to LCIG subjects who will not transition to commercial LCIG and have study device removed.

The following Study Day windows for Extension Period will be used to assign safety assessments to planned study visits for LCIG subject entering Extension Period.

Table 3. Analysis Windows for Safety Variables During the Extension/Transition Period for the LCIG Group

Assessment	Planned Visit	Nominal Study Day	Study Day Range ^a

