Vital signs and weight, Clinical labs ^a , Electrocardiograms ^a , and special labs	Baseline ^b		≤ date of last visit in 26-week randomized treatment period for subjects randomized to LCIG group.
	Month 3 ^c	84	1 – 126
	Month 6	168	127 – 200
	Every 3 months following until subjects' transition to commercial LCIG	Previous + 84	Previous lower bound + 84 through previous upper bound + 84

- a. Clinical labs and Electrocardiograms will not be collected during the Transition Period.
- b. Baseline refers the baseline of Extension Period. All days refer to study day in Extension Period. All post-baseline assessments must also be no more than 1 day after the final PEG-J removal for subjects who have their study device removed after their last infusion of Study M12-927 LCIG.
- c. Applicable only to US subjects.

The following Study Day windows for Extension Period will be used to assign safety assessments to planned study visits for OMT subject entering Extension Period.

Table 4. Analysis Windows for Safety Variables During the Extension/Transition Period for the OMT Group

Assessment	Planned Visit	Nominal Study Day	Study Day Range ^a
Vital signs and weight,	Baseline ^a		< date of NJ/PEG-J placement for subjects randomized to OMT group and entering Extension Period
	Week 2	14	2 – 28
	Week 6	42	29 – 63
	Month 3	84	64 – 126
	Month 6	168	127 – 200
	Every 3 months following until subjects' transition to commercial LCIG ^c	Previous + 64	Previous lower bound + 84 through previous upper bound + 84
Clinical labs ^b , Electrocardiograms ^b , and special labs	Baseline ^a		< date of NJ/PEG-J placement for subjects randomized to OMT group and entering Extension Period
	Month 3	84	2 – 126
	Month 6	168	127 – 252
	Every 3 months following until subjects' transition to commercial	Previous + 168	Previous lower bound + 168 through previous upper bound + 168

a. Baseline refers the baseline of Extension Period. All days refer to study day in Extension Period. All post-baseline assessments must also be no more than 1 day after the final PEG-J removal for subjects who have their study device removed after their last infusion of Study M12-927 LCIG.

b. Clinical labs and Electrocardiograms will not be collected during the Transition Period.

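### SAP Table 3 gives the first 12-week Transition visit of LCIG subjects outside the US no analysis window (minor; descriptive by-visit safety tables only)

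*SAP*

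**What the plan says.** SAP 6.4, Table 3 is titled "Analysis Windows for Safety Variables During the Extension/Transition Period for the LCIG Group". Its windows run as follows: Month 3, nominal Day 84, Days 1-126; Month 6, nominal Day 168, Days 127-200; then further three-monthly windows until conversion to commercial LCIG, each defined as "Previous lower bound + 84 through previous upper bound + 84". Footnote a states that "Clinical labs and Electrocardiograms will not be collected during the Transition Period", which leaves vital signs, weight and special labs. Footnote c limits the Month 3 row: "Applicable only to US subjects".

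Other places are narrower than the title. The sentence introducing Table 3 speaks of "planned study visits for LCIG subject entering Extension Period", and footnote b ties the table's baseline and day count to the Extension Period. SAP 6.2 defines the day-count origin in the same way: "For LCIG subjects who enter the Extension Period, treatment start reference date in extension period (REFDT2) equals REFEDT1". SAP 6.3 gives the continuing-period baseline only for LCIG subjects who enter the Extension.

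On visits, SAP 4.2 opens the Extension Period to subjects in the United States and South Korea only. US LCIG subjects have visits at 3 and 6 months, and South Korean LCIG subjects every 6 months. For subjects continuing LCIG until commercial supply, SAP 4.2 (Part 4) says "Additional visits every 12 weeks from Week 26 will be scheduled to monitor subject safety". Protocol 5.1.3, under Commercial Transition Visits, has the same rule: "Additional visits every 12 weeks from Week 26 will be schedule to monitor subject safety".

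**The concern.** Footnote c fits the difference between the US and South Korea within the Extension Period, because only the US schedule has a 3-month visit. It does not fit the Transition Period, which is also in the table's title and has a visit at 12 weeks. Applied literally, it leaves that visit without a planned visit to belong to.

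SAP 10.3.1 and 10.4.1 promise mean change from the Extension/Transition baseline to each planned visit. A Month 3 row in those tables would contain US Extension subjects only, under a label that suggests Transition subjects are included. SAP 6.4 also states that its midpoint rule is meant to place every observation at a planned visit, so the footnote works against the section's own rule. A programmer would have to drop collected data or depart from the SAP.

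**Working it through.** **Inputs.** Table 3 windows and footnotes (SAP 6.4). Transition visits every 12 weeks from Week 26 (SAP 4.2, SAP Appendix A footnote b, Protocol 5.1.3). Visit tolerance of 7 days either way from the Week 6 visit onward (Protocol 5.3.1); applying it to Transition visits is an assumption.

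**1. The plan's own bound.** The midpoint between nominal Days 84 and 168 is (84 + 168)/2 = 126. This reproduces the printed upper limit of Month 3, so the row was built for visits 12 weeks apart.

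**2. Windows open to each group.** From Month 6 onward the bounds are 127-200, then 127 + 84 = 211 to 200 + 84 = 284, then 295-368. US subjects also have 1-126.

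**3. Assigning the 12-weekly visits**, counting days from the start of the continuing period:

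| Visit | Day (with 7 days either way) | US subject | Transition subject outside the US |
|---|---|---|---|
| 12 weeks | 84 (77-91) | Month 3 | none |
| 24 weeks | 168 (161-175) | Month 6 | Month 6 |
| 36 weeks | 252 (245-259) | 211-284 | 211-284 |
| 48 weeks | 336 (329-343) | 295-368 | 295-368 |

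The US column shows only how the windows behave; the US Extension itself lasts at most 6 months. The 7-day tolerance does not matter to the result, since any Transition visit before Day 127 is unassigned.

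**4. Does Table 2 catch the visit?** On the randomized-period day count it falls at 182 + 84 = Day 266. The last special-labs window there is 134-231, so it is outside. The vital-signs row for the Week 27 follow-up is 187-301, which contains Day 266, but its footnote b restricts that row to subjects who will not transition to commercial LCIG and have the device removed. Table 2 does not help.

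**5. Was Table 3 meant for Transition subjects?** The title and footnote a say so. The last row points the same way. It steps by 84 days after Month 6, while the US Extension ends by 6 months and South Korean LCIG visits are 6 months apart. Only the Transition schedule has 12-week steps beyond that point. So the table provides for the second and later Transition visits and closes the first.

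**6. The narrower reading.** If the lead-in and footnote b govern, Table 3 does not apply to Transition subjects at all. They then have no window table, no stated day-count origin and no stated baseline for the by-visit analyses in SAP 10.3.1 and 10.4.1. The 12-week visit is unassigned on either reading.

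**7. What does not depend on the window.** Minimum, maximum and final values are taken over the whole period (SAP 6.3, 10.3.1, 10.4.1). PCS vital-sign and weight values are counted at any observation in the period (SAP 10.4.3). These summaries share the baseline that SAP 6.3 leaves unstated for Transition subjects, but no observation drops out of them because of footnote c.

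**The case against.** The strongest reply is that footnote c is correct within the scope that the lead-in, footnote b and REFDT2 set, namely the Extension Period, and that the real slip is a disagreement about scope. That stands in part: the inconsistency is wider than one footnote, and rewording the footnote alone would not repair it. It does not remove the gap, because on that scope Transition subjects have no windows at all.

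A second reply is that the intended assignment is easy to recover, since the midpoint arithmetic gives 126 and SAP 6.7 foresees a derived dataset specification. That is fair as to intent. But footnote c is an explicit exclusion, and a programming specification should not have to override it.

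A third reply is that little is at stake, and this stands. The by-visit Extension/Transition tables are descriptive, and the group comparisons of these variables concern the 26-week period.

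A reader might infer three stronger things. The documents do not support them:

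- *That most countries lose the only on-treatment safety visit after Week 26.* The protocol plans approximately 10 countries, and two of them have an Extension, but a count of countries is not a count of subjects. Neither document says how long Transition lasts. Subjects who convert before Day 84 have no 12-week visit to lose.
- *That monitoring of weight loss or polyneuropathy is weakened.* SAP 10.2.3 defines these events of special interest by MedDRA searches of adverse events, not by visit windows, and SAP 10.2.1 summarises Transition adverse events separately.
- *That the data are lost.* They are collected and used in the summaries listed in step 7.

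**Conclusion.** The point holds as a minor inconsistency in the SAP. For LCIG Transition subjects outside the US, the first 12-week visit (about Day 84) has no analysis window, so its vital signs, weight and special labs are absent from the by-visit Extension/Transition tables. A subject who converts after that visit but before Day 127 contributes to no planned visit. One who stays to Week 24 contributes one of two.

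The number of subjects is not known from the documents. It could be zero, and it is at most a part of the approximately 44 planned for LCIG. No primary, key secondary or other 26-week analysis changes, and neither do the event-of-special-interest summaries.

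The conclusion rests on two readings: that the Transition column of the activity tables (Protocol Table 3, SAP Appendix A) schedules vital signs, weight and special labs, which footnote a of SAP Table 3 supports; and that the continuing period is counted from the day after the randomized period ends, as SAP 6.2 does for the Extension.

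**What to change.** - SAP Table 3, footnote c: change to *Not applicable to South Korea subjects (visits every 6 months)*. This keeps its evident purpose and opens Days 1-126 to US Extension subjects and all Transition subjects.
- SAP Table 3, lead-in sentence and footnote b: refer to the Extension/Transition Period, in line with the title.
- SAP 6.2: state that REFDT2 equals REFEDT1 also for LCIG subjects in the Transition Period.
- SAP 6.3: extend the LCIG continuing-period baseline rule to the same subjects.

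The cost is a few phrases in the SAP and the matching programming. No new data, visits or protocol change are needed.

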6.5 Analysis of Vital Signs by Planned Time

Vital sign measurements were to be performed at hourly intervals on the first day of LCIG infusion via NJ and via PEG-J. Observations on the first day of LCIG infusion will be assigned to a planned time based on the time of assessment relative to the reported start time of the first LCIG infusion as follows.

Table 5. Analysis Windows for Vital Signs on the Day of LCIG Infusion for the LCIG Group

Planned Time	Nominal Relative Time (Minutes)	Relative Time Range (Minutes)
Hour 0	0	≤ 0
Hour 1	60	> 0 – 90
Hour 2	120	91 – 150
Hour 3	180	> 150

6.6 Adverse Event Analysis by Study Week

Treatment-emergent adverse events will be assigned to study week intervals based on the Study Day of onset as follows.

Table 6. Analysis Windows for Treatment Emergent Adverse Events During the 26-Week Treatment Period

Study Week(s)	Study Day Range
Week 1	1 – 7
Week 2	8 – 14
Week 3	15 – 21
Week 4	22 – 28
Week 5	29 – 35
Weeks 6 – 26	36 – 182

6.7 Derived Datasets

The study database will include the following derived datasets which will be used for the analyses described in this SAP.

- Subject Characteristics for all subjects who participated in the study: one record per subject with demographic, baseline characteristic, analysis population and subgroup variables.
- Study Drug Exposure during the 26-week randomized Treatment Period for the Safety Dataset: For LCIG subjects, one record per subject for each

exposure variable (morning dose, extra dose, etc.) and each planned assessment time with the prescribed dose and actual dose. For OMT subjects, one record per subject per medication.

- Efficacy Endpoints for the All Randomized Dataset: one record per subject for each variable and each planned assessment time with the baseline value, time point value, and change from baseline value for the NMSS, PDSS-2, UPDRS, PDQ-8, CGI-C, PGIC, PAS, GDS-15 and King's PD Pain Scale total and domain scores.

A Derived Dataset Specification that includes a detailed description of the dataset's structure and variables will be developed for each derived dataset.

7.0 Subject Disposition, Baseline Characteristics and Concomitant Medications

7.1 Subject Disposition

An overall summary of the disposition of all screened subjects will be prepared. The total number of subjects in each of the following categories as well as the number at each site will be presented:

- Screened, screen failed;
- Randomized to OMT group, prematurely discontinued treatment from OMT group, completed the planned 26 weeks of treatment in OMT group, continued to Extension Period, prematurely discontinued during the Extension Period, completed the Extension Period; Randomized to LCIG group, no NJ/PEG-J placed, NJ placed, prematurely discontinued during NJ, PEG-J placed, prematurely discontinued treatment during PEG-J, completed the planned 26 weeks of treatment in LCIG group, continued to Extension Period, prematurely discontinued during the Extension Period, completed the Extension Period.

An additional summary of screen failures will be prepared with the number and percentage of screened subjects who screen failed overall and for each specific screen failure reason.

Additional summaries of premature study drug discontinuations during the 26-week Treatment Period for both treatment groups, and during the Extension/Transition Period, will be prepared for the Safety Dataset with the number and percentage of subjects who prematurely discontinued for any reason, for each specific primary reason, and for each specific reason.

A listing will be prepared of all randomized subjects who are not included in the primary efficacy analysis. The listing will include each subject number and reason for exclusion.

7.2 Demographic and Baseline Characteristics

The following demographic and baseline characteristics will be summarized by treatment group and for overall subjects in the safety dataset unless otherwise specified.

- Gender (male/female)
- Race (white, black, American Indian/Alaska native, native Hawaiian or other Pacific Islander, Asian, Other, Multi-Race)
- Ethnicity (Hispanic or Latino, ne)
- Age (years)
- Age category (< 65, ≥ 65)
- Age category (< 75, ≥ 75)
- Weight for all subjects (kg)
- Weight for all male subjects (kg)
- Weight for all female subjects (kg)
- Height (cm)
- Body mass index (BMI, kg/m²)
- Body mass index category (< 25 kg/m², ≥ 25 kg/m²)
- Mini-Mental State Examination (MMSE) total score

- Parkinson's disease duration (years)
- Motor fluctuation duration (years)
- Parkinson's disease duration category (< 10 years, ≥ 10 years)
- Time from Parkinson's disease diagnosis to start of first levodopa medication (years)
- Proportion of subjects meeting each of the following United Kingdom Parkinson's Disease society (UKPDS) Brain Bank diagnostic criteria for PD
 - Diagnosis of bradykinesia
 - Diagnosis of muscular rigidity
 - Diagnosis of 4 – 6 Hz resting tremor
 - Diagnosis of postural instability

Alcohol and nicotine use will also be summarized. For alcohol use the number and percentage of subjects who are drinkers, ex-drinkers and non-drinkers (defined as those who have never been a drinker) will be presented. For nicotine use the number and percentage of users, ex-users and non-users (defined as those who have never been a user) will be presented. A subject reporting multiple use categories for the different types of nicotine (cigarettes, pipes, cigars and chewing tobacco) will be counted in the nicotine use category closest to user.

Categorical variables will be summarized with the number and percentage of subjects in each category. Continuous variables will be summarized with descriptive statistics (number of non-missing observations, mean, standard deviation, median, minimum and maximum).

